10.3.3 Pharmacokinetic Analyses for BMS-986207, Nivolumab, and Ipilimumab

Endpoint	Statistical Analysis Methods
BMS-986207	
Cmax, AUC(0-T), AUC(TAU), Ctau, CLT, Css-avg, AI_AUC, and T-HALFeff_AUC	Summary statistics: geometric means and coefficients of variation
Cmax, AUC(0-T), AUC	Scatter plots vs dose for each cycle measured; dose proportionality based on a power model and a CI around the power coefficient

Tmax. Summary statistics: medians and ranges

Nivolumab and Ipilimumab

Abbreviations: AI_AUC, accumulation index ratio of AUC at steady state to that after the first dose; AUC(0-T), area under the concentration-time curve from time zero to the time of the last quantifiable concentration; AUC(TAU), area under the concentration-time curve in one dosing interval; CI, confidence interval; CLT, total body clearance; Cmax, maximum observed concentration; Css-avg, average concentration over a dosing interval (AUC(TAU)/tau); Ctau, observed concentration at the end of a dosing interval; [REDACTED] T-HALFeff, effective elimination half-life that explains the degree of accumulation observed for a specific exposure measure; Tmax, time of maximum observed concentration.

PK time-concentration data may be pooled with data from other studies for population PK analysis, which will be presented in a separate report.

10.3.4 Immunogenicity

Endpoint	Statistical Analysis Methods
Incidence of ADA to BMS-986207, [REDACTED] [REDACTED] Baseline ADA-positive participant is defined as a participant who has an ADA-detected sample at baseline ^a ADA-positive participant is a participant with at least 1 ADA-positive sample relative to baseline after initiation of the treatment	Frequency distribution of baseline ADA-positive participants and ADA-positive participants after initiation of the treatment for each of BMS-986207, [REDACTED] [REDACTED].

Abbreviations: ADA, anti-drug antibody.

^a Baseline sample is the last sample before initiation of the treatment.

[REDACTED]

10.3.6 ECG Analyses

All ECG data analyses including summaries of each ECG parameter, frequency distribution of participants' maximum values/changes, and scatter plots will be performed following the current practice of ECG data analysis. Concentration-response analysis may be performed using mixed effect model, if appropriate (Part 1A). The details of ECG data analysis will be provided in the SAP.

10.3.7 Other Analyses

[REDACTED] analyses will be described in detail in the statistical analysis plan finalized before database lock. [REDACTED] at 1 year will be analyzed similarly to PFSR. The population PK [REDACTED] analysis may be presented separately from the main clinical study report.

10.3.8 Interim Analyses for Parts 2A, 2B, and 2C

The expansion phase of this study (Part 2A and Part 2B) employs a 2-stage design framework. Therefore, there will be an interim analysis as planned when an adequate number of participants have response-evaluable data. Additional interim analyses may also be performed for administrative purposes or publications. No formal inferences requiring any adjustment to statistical significance level will be performed.

For Part 2C, interim analyses may also be performed for administrative purposes or publications prior to the final database lock. No formal inferences requiring any adjustment to statistical significance level will be performed. Continuous safety monitoring will be implemented in Part

2C to further evaluate the safety of the triplet combination in the NSCLC population, in addition to that in Part 1C, as described below.

A Bayesian framework will be utilized for continuous monitoring of toxicity in Part 2C based on AEs meeting DLT criteria.⁴⁶ Observed incidence rates of treatment-related toxicities meeting DLT criteria (defined in [Section 7.4.1](#)) will be evaluated relative to a boundary (number of DLTs) associated with higher chance of the true DLT rate exceeding 33%.

Bayesian safety monitoring boundaries are established using a non-informative prior, Beta (0.5, 0.5). The posterior distribution is Beta ($0.5+n$, $0.5+(m-n)$), where m is number of treated Part 2C participants and n is the subset of these m participants who experience treatment-related toxicities meeting DLT criteria. All treated Part 2C participants are considered evaluable. The criterion for excess toxicity is based on a posterior probability (PP) of treated Part 2C participants with toxicities meeting DLT criteria $> 33\% \mid$ cumulative data exceeding 80%. If the criterion is met during continuous monitoring in Part 2C, there is greater than 80% PP that the DLT rate exceeds 33%; based on the observed data, the dose level may be re-evaluated and, based on the totality of data, a lower dose may be administered to the remaining participants. The cutoff number of participants with DLT needed to meet the criterion depends on the number of evaluable participants, with a final boundary of 14 participants with a DLT out of 37 or more.

Table 10.3.8-1: Safety Monitoring Boundaries for AEs Meeting DLT Criteria in Part 2C

Number of evaluable participants	Minimum Number of participants with AE meting DLT criteria
4 -6	3
7-8	4
9-11	5
12-14	6
15-17	7
18-19	8
20-23	9
24-26	10
27-29	11
30-32	12
33-36	13
37-39	14

Abbreviations: AE = adverse event; DLT, dose limiting toxicity.

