Part 2C will enroll a minimum of 20 participants per dose level of BMS-986207. One or two doses are planned to be evaluated and selected from the range of doses assessed as tolerable and not exceeding the maximum tolerated dose in Part 1C. If two doses will be tested at the Sponsor's discretion, participants will be randomized in a 1:2 ratio schema between the highest dose selected in Part 1C and the next lower dose, after at least 10 participants will have been tested at the dose found safe in Part 1C.

Continuous evaluation of toxicity events will also be performed in this part of the study. If, at any time, the aggregate rate of treatment-related toxicities meeting DLT criteria exceeds 33% in Parts 2A or 2B, the findings will be discussed and further enrollment may be interrupted. In addition, a more guided continuous safety monitoring will be implemented in Part 2C, 1L NSCLC expansion, using a Bayesian framework and specific criteria based on a posterior probability of a DLT rate exceeding 33% implemented starting with n=6 ([Table 10.3.8-1](#)). Depending on the nature and

grade of the toxicity, and after assessing the risk/benefit ratio, a new BMS-986207 dose for all participants, including those currently on treatment, may be initiated at a lower dose level.

Participants with an outcome of unconfirmed progressive disease, stable disease (SD), partial response (PR), or complete response (CR), at the end of a given cycle, will continue to the next treatment cycle. Participants will be allowed to continue study treatment until the first occurrence of any of the following:

- Completion of the maximum number of cycles
- Confirmed PD (see [Section 5.1.4](#))
- Clinical deterioration suggesting that no further benefit from treatment is likely
- Intolerability to therapy
- Participant meets criteria for discontinuation of study treatment as shown in [Section 8.1](#)

5.1.2.8 *Treatment with Additional Cycles Beyond 24 Weeks (Parts 1A, 1B, 2A, and 2B)*

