10.1.3.2 Cohort Expansion in Part 2C

Part 2C will be an expansion phase of the BMS-986207 in combination with nivolumab and ipilimumab in participants with advanced treatment-naïve NSCLC whose tumor cells express $\geq 1\%$ PD-L1.

The sample size for Part 2C is based on assessing an initial [REDACTED] activity signal as estimated by the ORR following treatment in the triplet combination arm and to provide additional information for the safety profile in the 1L NSCLC population.

One or two doses are planned to be evaluated in Part 2C and a minimum of 20 participants are enrolled per dose level of BMS-986207. So approximately 40 evaluable participants in total with 1L NSCLC with tumor cell PD-L1 expression of $\geq 1\%$ will be treated with BMS-986207 in combination with nivolumab and ipilimumab.

In the event pre-existing PD-L1 results are not confirmed by the central lab test, additional participants (up to 20%) will be enrolled to achieve a sample size of 40 evaluable participants.

The following Bayesian posterior probability (PP) criteria will be used to assess signal of anti-tumor activity with benchmark of 36% as unfavorable ORR and 56% as desirable ORR:^{44,45}

- An [REDACTED] activity signal is based on ORR satisfying the dual criteria: PP (ORR ≥ 0.56) $\geq 40\%$ and PP (ORR ≥ 0.36) $\geq 80\%$
- A lack of activity signal is based on ORR meeting the criterion: PP (ORR ≥ 0.36) $< 20\%$

A beta prior distribution beta (1, 1) for ORR and Binomial Bin (n, ORR) likelihood for number of responders were used.

Based on the above criteria, for each dose level a total of 20 evaluable participants in Part 2C will provide approximately 6.5% chance to show [REDACTED] activity when a true ORR is 36%, and at least 63% chance of showing activity signal if the true ORR is 56% or more (see [Table 10.1.3.2-1](#))

The ORR thresholds for efficacy signal (responders $\geq 11/20$) and lack of efficacy ($\leq 6/20$) and the operating characteristics of the posterior probability criteria are shown in [Table 10.1.3.2-1](#).

Table 10.1.3.2-1: Operating characteristics of criteria for antitumor activity by ORR

Sample Size	True ORR	PP (Activity)	PP (No Activity)	PP (Inconclusive)	Responder Cutoff Activity/ No Activity
20	0.3	0.017	0.416	0.566	11/6
20	0.36	0.065	0.217	0.718	11/6
20	0.5	0.412	0.021	0.567	11/6
20	0.56	0.626	0.005	0.369	11/6
20	0.6	0.755	0.002	0.243	11/6
22	0.3	0.014	0.313	0.673	12/6
22	0.36	0.058	0.14	0.801	12/6
22	0.5	0.416	0.008	0.576	12/6

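### If Part 2C tests two BMS-986207 doses, its toxicity rule pools them, so one dose can meet the plan's own criterion unflagged and a crossing does not show which dose caused it

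*Combined protocol and SAP*

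**What the plan says.** Section 5.1.2.7 describes Part 2C as a one- or two-dose part: "One or two doses are planned to be evaluated and selected from the range of doses assessed as tolerable" in Part 1C. It sets a minimum of 20 participants per dose level. If there are two doses, allocation is 1:2 between the highest selected dose and the next lower one, after at least 10 participants have been tested at the dose found safe in Part 1C. Section 10.1.3.2 gives a total of about 40 evaluable participants and judges activity separately by dose: "for each dose level a total of 20 evaluable participants in Part 2C will provide" the stated operating characteristics.

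The toxicity rule in Section 10.3.8 has no such qualifier. The posterior is Beta(0.5 + n, 0.5 + m − n), "where m is number of treated Part 2C participants and n is the subset of these m participants" with treatment-related toxicities meeting DLT criteria. It adds: "All treated Part 2C participants are considered evaluable". The criterion is a posterior probability above 80% that the DLT rate exceeds 33%. There is one table, Table 10.3.8-1, ending "with a final boundary of 14 participants with a DLT out of 37 or more".

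Sections 10.3.8 and 5.1.5 both refer to a single dose under evaluation. Section 5.1.2.7 says that after excess toxicity "a new BMS-986207 dose for all participants, including those currently on treatment, may be initiated at a lower dose level". Section 10.3.2 lists DLT rate by dose level as a descriptive summary. In Part 1C, Table 5.1.2.6-1 counts DLTs at the current dose.

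**The concern.** The efficacy rule was written for two doses and the toxicity rule was not. A table that runs to 39 fits the Part 2C total of about 40, a size that two doses of 20 reach only when pooled.

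Two things follow if two doses are tested. First, when the lower dose produces fewer DLTs it dilutes the count, so the rule can stay silent while one dose, taken alone, meets the 80% criterion. Second, when the pooled count does cross, the rule cannot tell an excess at one dose from a moderate rate at both. Part 2C is meant partly to inform the RP2D choice between doses, so both the safety signal and its attribution matter.

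**Working it through.** **Inputs from the plan.** Prior Beta(0.5, 0.5), threshold 33%, cut-off 80% and the printed boundaries (10.3.8, Table 10.3.8-1); monitoring from n = 6, at least 20 per dose and 1:2 allocation (5.1.2.7); about 40 in total (10.1.3.2).

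**Formula.** PP = P(p > 0.33), where p follows Beta(0.5 + n, 0.5 + m − n).

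**The plan's own figure.** At m = 20 the printed boundary is 9. The formula gives PP = 0.752 at 8/20 and 0.872 at 9/20, so 9 is reproduced. The last row is not: 14/37 gives 0.738 and 14/39 gives 0.656, both under 80%. That is a separate matter. The printed boundary is used below, with 14 carried to m = 40 because the text says 37 or more. By the stated criterion the boundary at 40 would be 16 (15/40 gives 0.731, 16/40 gives 0.827).

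**Dilution.**
- Higher dose 9/20: PP 0.872, criterion met.
- Lower dose 4/20: PP 0.105.
- Pooled 13/40: PP 0.481, below 14, so no signal.
- 11/20 with 2/20 (0.979 and 0.009) is also 13/40 and also gives no signal.

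**Attribution.** A pooled 14/40 may be 7 + 7 (0.585 at each dose), 10 + 4 (0.944 and 0.105) or 12 + 2 (0.994 and 0.009). The rule treats these alike.

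**How often it matters.** Assumptions: the first 10 Part 2C participants receive the higher dose, then 30 are randomised 1:2. That gives 10 + 30/3 = 20 at the higher dose and 30 × 2/3 = 20 at the lower. There is a look after every participant from n = 6, on the printed table, with 400,000 simulated trials per scenario. The true rates are assumptions; the documents give none.

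| True DLT rates (higher/lower) | Cross in lead-in | Whole trial: pooled vs higher dose alone | Trials not crossing in lead-in: pooled vs higher dose alone |
|---|---|---|---|
| 45%/20% | 65% | 78% vs 82% | 37% vs 50% |
| 50%/15% | 75% | 84% vs 91% | 34% vs 63% |
| 40%/30% | 53% | 78% vs 71% | 52% vs 37% |
| 36%/24% | 44% | 61% vs 59% | 30% vs 26% |

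The columns agree. At 45%/20%, 65% + 35% × 37% = 78% and 65% + 35% × 50% ≈ 82%. At 50%/15%, 75% + 25% × 34% ≈ 84% and 75% + 25% × 63% ≈ 91%.

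With boundaries recomputed from the 80% criterion, the last column becomes 25% vs 46% at 45%/20% and 23% vs 59% at 50%/15%.

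**Cost of per-dose counting** (chance that some boundary crosses, printed table). Both rates 20%: 15% pooled, about 25% with a boundary on each dose. Both rates 25%: 31% pooled, 44% per dose. Keeping the pooled check as well makes these about 26% and 46%.

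**The case against.** The strongest reply is that the practical loss is moderate. In the assumed design the count contains only the higher dose during the lead-in, and 65% to 75% of trials in the wide-gap scenarios cross there. Over the whole trial the difference is 4 points at 45%/20% and 7 at 50%/15%. With a small gap, pooling adds information and crosses as often or more often. This stands. A reader who saw only the figures after the lead-in might infer that pooling roughly halves detection; the whole-trial figures do not support that.

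A reader might also infer that DLT rates at the two doses are expected to differ. The documents do not say so. Section 3.2.1.4 reports no relationship between adverse events and BMS-986207 dose, alone or with nivolumab. The 2 DLTs in 4 evaluable participants in the triplet occurred at 1200 mg, a dose no longer being tested. Both Part 2C doses must first be assessed as tolerable in Part 1C. A true rate of 45% to 50% is therefore an unfavourable case.

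Safeguards exist. The study is open-label, signal detection is at least monthly (5.1.5), DLT rate is tabulated by dose (10.3.2), and a crossing is advisory, weighed with all the data. Those monitoring safety can therefore see which dose is involved. None of this is a pre-specified per-dose criterion, and that gap remains.

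Finally, a second dose is at the sponsor's discretion. With one dose the point does not arise.

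**Conclusion.** The point holds, conditional on two doses being tested. As written, the rule pools them, can be silent when one dose meets its own criterion, and does not attribute a crossing. The size is modest over the whole trial (78% vs 82%, and 84% vs 91%) and larger once randomisation has begun (37% vs 50%, and 34% vs 63%, among the 35% and 25% of trials still uncrossed). It reverses when the doses have similar DLT rates.

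These figures rest on assumed true rates and on the lead-in being 10 Part 2C participants at the higher dose, which 5.1.2.7 does not state outright. Without a Part 2C lead-in (13 higher, 26 lower) the gap at 50%/15% would be 34% vs 82%, but 13 would miss the plan's minimum of 20 per dose.

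The documents do not support reading this as a rule that leaves participants unmonitored, or as one that forces a dose change on everyone: the action in 5.1.2.7 is optional and follows a risk/benefit assessment.

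**What to change.** In 10.3.8, define m and n per BMS-986207 dose level: treated Part 2C participants at that dose, and those among them with toxicities meeting DLT criteria. Apply the same prior, 33% threshold and 80% criterion to each dose, and say that a crossing prompts re-evaluation of that dose level. Keep the pooled count as a second check, since it is the more sensitive one when the rates are close. Reconcile the single-dose wording in 10.3.8 and 5.1.5, and the reference to all participants in 5.1.2.7, with a two-dose Part 2C. State whether the 10 lead-in participants belong to Part 2C. No dose or clinical action is proposed here.

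The change is to wording only; the smaller rows of Table 10.3.8-1 already cover 20 per dose. The price is the higher false-alarm rate shown above, which the protocol should report. It is tolerable because a crossing leads to re-evaluation and not to an automatic stop.

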7.4.1 Dose Limiting Toxicities

For the purpose of guiding dose escalation, DLTs will be defined based on the incidence, intensity, and duration of AEs for which no clear alternative cause is identified. The DLT period will be 28 days (4 weeks) in Parts 1A and 1B. The DLT period for Part 1C will be 42 days (6 weeks).

For the purpose of participant management, any AE that meets DLT criteria, regardless of the cycle in which it occurs, will lead to discontinuation of study drug unless the Investigator determines that only 1 of the agents must be discontinued due to toxicity attributed to that agent alone. Participants who withdraw from the study during the 4-week DLT evaluation period (6-week DLT evaluation period for Parts 1C and 2C) for reasons other than a DLT may be replaced with a new participant at the same dose level. The incidence of DLTs during the 4-week DLT evaluation period (6-week DLT evaluation period for Parts 1C and 2C) will be used in dose escalation decisions and to define the MTD. AEs occurring after the 4-week DLT period (6-week DLT evaluation period for Parts 1C and 2C) will be considered for the purposes of defining the RP2D upon agreement between the Sponsor, Medical Monitor, and Investigators.

Participants experiencing a DLT will not be retreated with study drug, and will enter the safety follow-up period of the study. DLTs occurring after the 4-week (or 6-week period for Parts 1C and 2C) DLT observation period will be accounted for in determining the RP2D for expansion.

AEs will be graded according to the NCI CTCAE v4.03.

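### Part 2C toxicity monitoring counts participants still inside the 6-week DLT period as completed non-DLTs, so during accrual the posterior is too low and the boundary can be crossed late

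*Combined protocol and SAP*

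**What the plan says.** Section 10.3.8 states the intent: "A Bayesian framework will be utilized for continuous monitoring of toxicity in Part 2C based on AEs meeting DLT criteria". The posterior is Beta(0.5+n, 0.5+(m−n)), "where m is number of treated Part 2C participants and n is the subset of these m participants" who have had a treatment-related toxicity meeting DLT criteria. The section then adds: "All treated Part 2C participants are considered evaluable". It sets no minimum follow-up, no weight for participants still under observation and no pause in accrual. Excess toxicity is flagged when the posterior probability of a rate above 33% is more than 80%. Table 10.3.8-1 turns this into counts, "with a final boundary of 14 participants with a DLT out of 37 or more". Section 5.1.2.7 describes the same monitoring as a "posterior probability of a DLT rate exceeding 33% implemented starting with n=6".

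Section 7.4.1 gives Part 2C a DLT window. Incidence in the "6-week DLT evaluation period for Parts 1C and 2C) will be used in dose escalation decisions and to define the MTD". Part 1C, with the same triplet and the same window, counts only DLT-evaluable participants (Section 5.1.2.6, Table 5.1.2.6-1).

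**The concern.** The term m−n in the posterior is the number of observed non-events. With m set to all treated, a participant on day 1 of 42 adds as much evidence of safety as one who finished the window without a DLT. The share of unfinished participants is largest while accrual is fastest, which is when a continuous rule is most needed. A participant who leaves on day 10 without a DLT also counts as a full non-event, and does so permanently.

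The trial's own data show that the denominator can matter. At 1200 mg in Part 1C, 6 participants were treated, 4 were DLT-evaluable and 2 had DLTs. In Table 5.1.2.6-1, 2 of 4 means de-escalate and 2 of 6 means stay. That is the Part 1C rule, not the Part 2C rule, but Part 2C adopts the denominator that would have changed that reading.

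At stake is how many participants are treated before the dose is re-examined, and whether the rule performs the same whatever the enrollment speed.

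**Working it through.** **Inputs.** From Section 10.3.8: prior Beta(0.5, 0.5), threshold 33%, cut-off 80%, and the counts in Table 10.3.8-1. From Section 7.4.1: a 42-day window. From Section 10.1.3.2: about 40 participants. From Section 5.1.2.7: looks start at 6. Accrual rate, true DLT rate and DLT timing are not in the documents and are assumed.

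**Step 1: the plan's own boundaries.** PP(n, m) = P(p > 0.33 | Beta(0.5+n, 0.5+m−n)), and the boundary is the smallest n with PP > 0.80. This reproduces the printed table for every m from 4 to 13, and at 18 of the 36 sizes from 4 to 39. At the other 18 the printed count is 1 or 2 below the stated rule: 6/14 gives 0.787, 9/23 gives 0.739, 14/37 gives 0.738 and 14/39 gives 0.656. The simulation below therefore uses the printed table, and the stated rule is given as a variant.

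**Step 2: direction.** Hold the DLT count fixed and add just-dosed participants:

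| Followed only | PP | Just-dosed added | PP | Printed boundary at the larger m |
|---|---|---|---|---|
| 3/6 | 0.815 | 3/7 | 0.720 | 4 |
| 3/6 | 0.815 | 3/9 | 0.525 | 5 |
| 5/11 | 0.812 | 5/14 | 0.597 | 6 |
| 9/20 | 0.872 | 9/26 | 0.578 | 10 |

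PP falls with every added non-event and the boundary never falls as m grows. Counting pending participants in full can therefore only leave the crossing unchanged or delay it. The two halves of the table are the extremes of weight 0 and weight 1. In the first row, a seventh participant with weight w gives P(p > 0.33 | Beta(3.5, 3.5+w)), which reaches 0.80 at w ≈ 0.16. Since 0.16 × 42 ≈ 7 days, that example applies to someone dosed within about the last week.

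**Step 3: size.** The simulation uses N = 40, Poisson accrual, DLT times uniform over 42 days, the printed table (14 kept at m = 40) and 3,000 trials per row. The comparator weights each participant without a DLT by the fraction of the window completed, with the effective m rounded up. Trials that never cross count as 40 treated.

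| Accrual per month | Mean treated at crossing, true rate 50%: plan | Weighted | Difference | P(cross), true rate 33%: plan | Weighted |
|---|---|---|---|---|---|
| 1 | 10.4 | 10.5 | −0.1 | 0.640 | 0.644 |
| 2 | 11.8 | 11.4 | 0.4 | 0.606 | 0.625 |
| 4 | 14.8 | 12.9 | 1.9 | 0.548 | 0.605 |
| 8 | 21.6 | 16.1 | 5.5 | 0.501 | 0.605 |

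Rounding up favours the plan. A separate printed-table run gave about 14 against 11 at 4 per month, a difference of 3. At 6 per month, a check run starting both rules at 6 treated gave 17.7 against 13.5 (effective m rounded up) or 12.2 (rounded down), a difference of 4.2 to 5.5. With the stated 80% rule in place of the table, the figures were 12.0 against 10.8 at 2 per month, 15.6 against 12.7 at 4 and 19.3 against 14.0 at 6.

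**Step 4: price.** At a true rate of 20% and 4 per month, the chance of ever crossing with the printed table rises from 6.4% to 10.8% (rounded up). Other codings start at about 5–7% and reach about 12–18%. With every outcome known at once, the crossing chance is 15.2% for the printed table and 13.5% for the stated rule.

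**Step 5: early leavers.** Leaving on day 10 without a DLT is 10/42 = 0.24 of a window, but is booked as 1 for the rest of the study.

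**The case against.** The rule is advisory: crossing leads to a re-evaluation on all the data, so a late crossing does not by itself expose anyone. Section 5.1.5 adds safety review at least monthly and ad hoc. Dilution by pending participants ends when their windows close. Section 10.3.8 puts no time limit on the numerator, so DLTs after week 6 also count, and the simulation omits them. From m = 14 the printed table is often lower than the stated rule, which offsets part of the delay: the stated rule at 30 followed needs 13, and the table at 36 treated also needs 13. All of this stands and limits the size. None of it helps at 6 to 13 participants, where table and rule agree.

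There may also be an earlier trigger. The synopsis, in its Part 2C text, calls for discussion if the aggregate rate of toxicities meeting DLT criteria exceeds 33% at any time. In one simulation at 4 per month and a true 50% rate, that raw trigger fired at a mean of 10.2 treated, ahead of 12.7 for the weighted rule. But Section 5.1.2.7 words the trigger for Parts 2A or 2B, and neither place defines its denominator, so it cannot be relied on as written.

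Two stronger readings are tempting. A reader might take 12 treated, 4 of them in the window and 4 DLTs, set this beside 4/8 (PP 0.847), and infer that a crossing has been hidden. That gives the four pending participants zero weight. At half weight the effective m is 10, PP is 0.69 and nothing is crossed. A reader might also infer that Section 7.4.1 obliges Part 2C monitoring to use completed windows. It ties the 6-week incidence to dose-escalation decisions and the MTD, not to expansion monitoring.

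**Conclusion.** The point holds as a bias of known direction and conditional size. While participants are pending, the posterior in Section 10.3.8 is too low for the follow-up actually accrued, and the boundary is crossed at the same time or later. With the printed table, a true DLT rate of 50% and uniform DLT times, the delay is about 0–2 participants at 1–2 per month, about 2–3 at 4 per month and about 5 at 6 per month or faster. At a true rate of 33%, the written rule's chance of crossing drifts from 0.640 to 0.501 as accrual goes from 1 to 8 per month, while the weighted rule stays between 0.605 and 0.644. The documents give no accrual rate, so they do not show that a material delay will occur in this trial, only that nothing in the rule prevents one. The pending part of the dilution is temporary; the part from early leavers is not.

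**What to change.** In Section 10.3.8, define m as the sum of weights: 1 for each participant with a DLT, and for each participant without one the fraction of the 42-day window completed, held at its value on the day of leaving for anyone who drops out. Compute the posterior probability directly, or state how a fractional m is rounded when reading the table. Once every window is complete, and with no early leavers, this is the current rule. State that DLTs after day 42 stay in the numerator if that is intended.

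Two simpler changes are not recommended. Counting DLTs at once but non-DLTs only at day 42 biases upward: at a true 20% rate and 8 per month, crossing is about 0.40 against about 0.03 under the plan. Waiting for full follow-up on everyone does not trigger sooner (15.0 against 14.8 treated at 4 per month and a true 50% rate).

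Reconcile Table 10.3.8-1 with the 80% criterion, then report operating characteristics for the boundaries finally adopted over a range of accrual rates. Reconcile the synopsis and Section 5.1.2.7 on whether the 33% aggregate trigger covers Part 2C, and define its denominator.

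The cost is a few lines of text and one simulation. The statistical price is the rise in crossings at a low true rate shown in Step 4. It mostly restores the rate the boundaries give with complete data, although some codings go slightly above it, and a crossing only prompts a re-evaluation.

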The purpose of Part 2C is to gather preliminary efficacy information regarding BMS-986207 in combination with nivolumab and ipilimumab in participants with advanced, treatment-naïve NSCLC whose tumors express [REDACTED] to assess optimal dose selection for RP2D. These subjects will be treated with BMS-986207 q3w at a dose not to exceed the dose declared tolerable in Part 1C, nivolumab 360 mg q3w, and ipilimumab 1 mg/kg q6w. Additional doses lower than the dose declared tolerable might be tested for dose optimization in Part 2C.

Part 2C may begin once there is sufficient safety data from a minimum of 6 participants in Part 1C.

Continuous evaluation of toxicity events will also be performed in this part of the study. If, at any time, the aggregate rate of treatment-related toxicities meeting DLT criteria exceeds 33%, the findings will be discussed and further enrollment may be interrupted. Depending on the nature and grade of the toxicity, and after assessing the risk/benefit ratio, a new dose for all participants may be initiated at a lower dose level.

Participants with an outcome of unconfirmed progressive disease, stable disease (SD), partial response (PR), or complete response (CR) at the end of a given cycle will continue to the next treatment cycle. Participants will be allowed to continue study treatment until the first occurrence of either: 1) completion of the maximum number of cycles, 2) confirmed PD, 3) clinical deterioration suggesting that no further benefit from treatment is likely, 4) intolerance to therapy, or 5) the participant meets criteria for discontinuation of study therapy. Individual participants with confirmed CR will be given the option to discontinue study therapy on a case-by-case basis after specific consultation and agreement between the investigator and BMS Medical Monitor in settings where benefit/risk justify discontinuation of study therapy.

Dose Limiting Toxicities: For the purpose of guiding dose escalation, DLTs will be defined based on the incidence, intensity, and duration of adverse events (AEs) for which no clear alternative cause is identified. DLT period will be 28 days (4 weeks) in Part 1A and Part 1B and 42 days (6 weeks) in Part 1C.

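### Table 10.3.8-1: at half the tabulated sizes the Part 2C toxicity boundary does not meet its own >80% posterior rule, and the flat final boundary of 14 falls to 29% at 48 treated

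*Combined protocol and SAP*

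**What the plan says.** Section 10.3.8 gives every input for the Part 2C toxicity monitor: a Beta(0.5, 0.5) prior, a Beta(0.5+n, 0.5+(m−n)) posterior, a 33% DLT-rate threshold and an 80% posterior cut-off. Here "m is number of treated Part 2C participants and n is the subset of these m participants" with toxicities meeting DLT criteria, and "All treated Part 2C participants are considered evaluable".

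The section says what a crossing means: "If the criterion is met during continuous monitoring in Part 2C, there is greater than 80% PP that the DLT rate exceeds 33" per cent. The dose level may then be re-evaluated and a lower dose may be given to the remaining participants.

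Table 10.3.8-1 prints the minimum DLT count for 4 to 39 evaluable participants, and the text closes the rule "with a final boundary of 14 participants with a DLT out of 37 or more". Section 5.1.2.7 starts the monitoring at 6 participants.

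The planned size is about 40 evaluable (Section 10.1.3.2). If pre-existing PD-L1 results are not confirmed centrally, "additional participants (up to 20%) will be enrolled to achieve a sample size of 40 evaluable participants".

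**The concern.** A table of posterior boundaries should follow from its stated prior, threshold and cut-off. Here the later rows look too low for an 80% cut-off: 14/39 is an observed rate of 35.9%, barely above 33%. A boundary held at 14 for any larger number must also lose meaning as the denominator grows.

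The section tells the team how strong the evidence is when a boundary is crossed, and dose reduction may follow. If that statement is false, one analyst using the table and another using the criterion will reach different answers on the same data. A dose could be lowered in a cohort that has efficacy as a primary objective and informs dose selection, on weaker evidence than the plan claims.

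**Working it through.** **Inputs.** Section 10.3.8: prior Beta(0.5, 0.5), threshold 0.33, cut-off 0.80, all treated participants counted. Section 5.1.2.7: monitoring from 6. Section 10.1.3.2: 40 evaluable plus up to 20%. The documents do not print a maximum number treated; I take 40 × 1.2 = 48.

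**Formula.** PP(n, m) = P(X > 0.33), where X follows Beta(0.5 + n, 0.5 + m − n). The boundary at m is the smallest n with PP > 0.80.

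**Where the plan's figures are reproduced.** The printed boundary agrees at m = 4–13, 15–16, 18–21, 24 and 27, which is 18 sizes. Examples: 3/6 gives 0.815, 5/11 gives 0.812, 8/19 gives 0.803.

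**Where they are not.** It is too low at m = 14, 17, 22–23, 25–26 and 28–39, the other 18 of 36 sizes. By row, 8 of 12 rows fail at one or more sizes, and the last three rows fail throughout. The shortfall is two DLTs at 36 and 39 and one elsewhere.

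| Printed boundary | PP | Stated rule needs |
|---|---|---|
| 6/14 | 0.787 | 7 |
| 7/17 | 0.767 | 8 |
| 9/23 | 0.739 | 10 |
| 10/26 | 0.728 | 11 |
| 11/29 | 0.719 | 12 |
| 12/32 | 0.711 | 13 |
| 13/36 | 0.660 | 15 |
| 14/37 | 0.738 | 15 |
| 14/39 | 0.656 | 16 |

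**Flat 14 beyond the table.**

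| m | PP at 14 | Observed rate | Stated rule needs |
|---|---|---|---|
| 40 | 0.613 | 35.0% | 16 |
| 43 | 0.483 | 32.6% | 17 |
| 48 | 0.290 | 29.2% | 19 |

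From m = 43 the posterior favours a rate at or below 33%, yet the rule still flags.

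**Is it another reading of the rule?** A threshold of 1/3 is worse (20 mismatches). A Beta(1, 1) prior leaves 15, a cut-off of 0.75 leaves 13, a cut-off of 0.70 leaves 10 and a threshold of 0.30 leaves 7. No combination in a grid of 11 priors, 8 thresholds and 9 cut-offs reproduced the whole table; the closest left 2 mismatches and was not the stated rule.

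**Direction.** One DLT below a printed boundary never gives PP above 0.772 (4/9). Staying under the table therefore always means the stated criterion is unmet for the pooled count.

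**Probability of ever crossing**, exact recursion from 6 participants:

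| True DLT rate | By 40, printed | By 40, stated rule | By 48, printed (14 flat) | By 48, stated rule |
|---|---|---|---|---|
| 25% | 0.31 | 0.26 | 0.42 | 0.26 |
| 30% | 0.52 | 0.43 | 0.69 | 0.44 |
| 33% | 0.65 | 0.55 | 0.81 | 0.57 |

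**Secondary, only if a second dose opens.** Section 5.1.2.7 then says that "participants will be randomized in a 1:2 ratio schema between the highest dose selected in Part 1C and the next lower dose", while m and n stay pooled. Ten DLTs in 20 at the higher dose alone give PP 0.94; adding 3 in 20 at the lower dose gives 13/40, PP 0.48, below 14.

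**The case against.** The strongest reply concerns consequence, not arithmetic. The boundaries err towards caution, crossing forces nothing, and no signal that meets the stated rule is hidden. Counting sizes also overstates what monitoring would meet: with the printed table to 40, 69% to 87% of first crossings have PP above 0.80 at true rates of 20% to 50%, because many crossings come early, where the table is right. All of that stands. It limits the harm but leaves 13% to 31% of first crossings without the stated meaning.

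The 29% figure needs 48 treated. Sections 5.2 and 7.2 give a different top-up rule: more than 25% discordant, to secure at least 30 confirmed. So 48 is an upper case. But the table already stops short of the planned 40, where 14 gives 0.613. If 48 are treated, 20% to 28% of crossings at true rates of 20% to 33% fall at 40 or later.

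The Part 2C synopsis text has its own trigger: if "the aggregate rate of treatment-related toxicities meeting DLT criteria exceeds 33%, the findings will be discussed and further enrollment may be interrupted". It needs fewer DLTs than the table at every m from 6 to 39 (7 against 9 at m = 20). If it applies, the chance of some trigger by 40 is 0.63 at a true 25% and 0.86 at 33% whichever table is used. Section 5.1.2.7, however, ties that trigger to Parts 2A or 2B and gives Part 2C the Bayesian table, so the table cannot be dismissed as redundant.

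Pooling across doses is a design trade-off. Section 10.3.2 already plans DLT rates by dose level, and the main point does not depend on it.

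**Conclusion.** The concern holds. For m = 4 to 39 it rests only on inputs printed in Section 10.3.8: 18 of 36 boundaries fail the >80% rule, with PP between 0.66 and 0.79 where they fail. At the planned 40 the flat 14 delivers 0.613. At 48, assuming the full 20% over-enrolment is treated, it delivers 0.290.

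The effect is earlier and more frequent re-evaluation, not missed toxicity. At an acceptable true rate of 25%, the chance of a flag rises from 0.26 to 0.31 by 40, and to 0.42 by 48. Those crossing probabilities describe the table alone and do not count the synopsis trigger.

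**What to change.** Choose one of two repairs.

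**(a) Recompute from the stated prior and 80% rule:** 4–6: 3; 7–8: 4; 9–11: 5; 12–13: 6; 14–16: 7; 17–19: 8; 20–21: 9; 22–24: 10; 25–27: 11; 28–29: 12; 30–32: 13; 33–35: 14; 36–38: 15; 39–40: 16; 41–43: 17; 44–46: 18; 47–48: 19. State that this lowers sensitivity: crossing by 40 at a true 33% falls from 0.65 to 0.55.

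**(b) Keep the more cautious printed table to 39.** Replace the >80% statement with the PP actually delivered (0.66 to 0.79 at the 18 sizes that differ). Replace the open-ended final boundary with explicit rows, for example 40–42: 15; 43–44: 16; 45–47: 17; 48: 18, all with PP above 0.65. This suits a sponsor who wants to keep the present sensitivity.

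Either way, state whether the synopsis >33% trigger applies to Part 2C. If the second dose opens, report the posterior by dose beside the pooled count. Acting on it has a price: with both doses at a true 25%, simulation puts any crossing at 42% to 44% instead of 26% to 31%.

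The cost is a recalculated table or a restated probability, plus the rows for 40 to 48. No extra patients or data are needed.
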